Activities- a) written self-reflection exercise; b) text and narrated video

Challenge 6: Watch Karl's epiphany

Activities- a) watch character video scene; b) text and narrated video

Challenge 7: Explore your values and priorities

Activities- a) written self-reflection exercise; b) text and narrated video

Challenge 8: Think about the end of life

Activities- a) written self-reflection exercise; b) text and narrated video

Challenge 9: Build a thriving community

Activity- written self-reflection exercise

Challenge 10: Watch Jim self-reflect

Activities- a) watch character video scene; b) text and narrated video

Challenge 11: Consider the benefits of mindfulness

Activity- text and narrated video

Challenge 12: Focus on your breath

Activity- text and narrated video

Challenge 13: Play video game

Activity- video game "*Mindful Living*"

Challenge 14: Link goal and meaning

Activity- written self-reflection exercise

Funny Video: *Know your weakness*

Skill 2: Know the issue

Challenge 1: Become informed

Activity- text and narrated video

Challenge 2: See how David ignores information!

Activity- a) watch character video scene; b) text and narrated video

Challenge 3: Discover your own biases

Activity- a) written self-reflection exercise; b) text and narrated video

Challenge 4: Master the basics of I COPPE

Activity- text and narrated video

Challenge 5: Play Stop Before You Shop

Activity- video game “*Stop Before You Shop*”

Challenge 6: Play True or False

Activity- video game “*True or False*”

Challenge 7: Play Well Words

Activity- video game “*Well Words*”

Challenge 8: Play Match the Task

Activity- video game “*Match the Task*”

Challenge 9: Select a BET I CAN strategy to match your goal

Activity- written self-reflection exercise

Funny Video: *Know what you're getting into*

Driver 7: Next Steps

Skill 1: Make a plan

Challenge 1: Imagine your best possible self

Activities- a) written self-reflection exercise; b) text and narrated video

Challenge 2: Turn your aspirations into goals

Activity- written self-reflection exercise

Challenge 3: Watch Karl clean up his act

Activities- a) watch character video scene; b) text and narrated video

Challenge 4: Make it gradual

Activities- a) text and narrated video; b) written self-reflection exercise

Challenge 5: Help Florence make it gradual

Activities- a) watch character video scene; b) text and narrated video

Challenge 6: Reinforce yourself

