7) **Fun For Wellness Experience Survey.** Only intervention group participants will be administered this self-report survey on one occasion after exposure to the intervention (30-days post baseline). This 15-item self-report survey measures user experience and evaluation across various feasibility and acceptability areas (e.g. enjoyment, usefulness, learning, relevance, modules, games, text, etc.). This data will guide future development of the intervention.

8) Participation measures

We will measure the amount of curriculum exposure by calculating the number of challenges each participant has completed. We will be able to use this measure to determine intervention dosage and compare effects based on dosage amount. Some other measures we will use to determine participant engagement include: time spent on each module, frequency of website visits, number of videos watched, number of games played, number of community forum visits, number of narrated videos observed, and number of overall visits to the online program.

Risk/Benefit Assessment

As far as we can tell, the potential risk to participants is minimal or non-existent. There are no risks that we can detect in participating in the program. The text and contents of the program are not offensive or controversial in any way. Participants may experience wellness benefits through participation in this study. By engaging in the curricular activities, participants will be prompted to focus on their internal awareness of their personal well-being across many areas of their lives. Through these activities, they may benefit by increasing their insight into what their current levels of satisfaction are in these life domains. This insight may potentially act as a motivator for a participant to improve their personal well-being.

Potential benefits of this research to society

The program we are seeking to test through this study will contribute to the promotion of well-being in at least two ways. First, effectiveness of the intervention will be measured using the recently validated I COPPE Scale as a self-assessment embedded in the program experience for each participant. Effectiveness findings will provide the researchers with more information on the sensitivity of the instrument, further informing the psychometric development of this tool.

IRB Study Number: TBD

Title: Patient Well-Being Research Project 01-23-17 to IRB

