Any confidential data that may be printed in hard copy form (paper) will be kept in the secured offices of the Principal Investigator, [name]. and/or Project coordinator, [name]. Only authorized research project staff will have access to hard copy data. [name] office is located at [name]. [name] office is located at [name].

Data Analysis Plan

Data Management & Quality Control Procedures. Procedures to ensure quality control in the collection, verification, and documentation of data have been established by the research team in our prior studies. Data files will be provided for statistical analyses in file formats which can be read by or translated into appropriate formats for the statistical programs that are planned to be used in this study.

Data Preparation & Preliminary Analyses. Testing of distributional assumptions will include statistical tests for univariate and multivariate normality (tests of skew & kurtosis) as well as visual inspections of the empirical distributions for the data at each time point. Should deviations be deemed sufficient for concern, transformation of variables (and/or estimation methods robust to deviations from conditional normality) will be used where possible. Reliability estimates of internal consistency (e.g., Cronbach's α) will be generated for scale scores.

Hypotheses and Methods

H1: Outcome effects: The online well-being program will be more effective than the wait-list control condition in improving: 1) overall well-being 2) domain well-being, and 3) health related quality of life (HRQOL) over time.

IRB Study Number: TBD

Title: Patient Well-Being Research Project 01-23-17 to IRB

These hypotheses will be conceptualized within the general multilevel structural equation modeling (MSEM; Muthén & Asparouhov, 2008) framework. Analyses will test separately for differences in linear and non-linear trajectories of well-being (overall and domain specific) over the assessment time points among the 2 conditions. Parameter estimates and attrition rates may inform Monte Carlo simulations (Muthén & Muthén, 2002) with 10000 replications to determine power (given sample size) for the regression of the slope growth factor on the dichotomous (i.e., treatment versus placebo control) intervention variable (Cohen, 1988; Raudenbush & Liu, 2001).

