Emotions	Cope with negative emotions	Yu-Hsin Liao et al (2012)	
 Effects of experiential self-focus writing on negative affect after an interpersonal hurt College students who had experienced interpersonal hurt were randomly assigned to experiential self-focus condition (write about feelings and experiences related to the hurt) or to control writing condition (write about neutral event) 	
 Negative affect resulting from an interpersonal hurt significantly decreased over time among participants in the experiential self-focus writing group compared with the control group.

Thoughts	Challenge assumptions	Hofmann et al (2009)	
 • Effect of reappraisal, acceptance, and suppression strategies on anxious arousal • Randomly assigned to one of three different emotion regulation strategies (Reappraisal, Suppression, or Acceptance) and asked to give an impromptu speech • The Reappraisal group was instructed to regulate their anxious arousal by reappraising the situation; the Suppression group was asked to suppress their anxious behaviors; and the Acceptance group was instructed to accept their anxiety 	
 • Overall, reappraisal was most effective strategy for regulating anxious arousal. • Both reappraising and accepting anxiety was more effective for moderating the physiological arousal than suppressing anxiety. • Reappraising was more effective for moderating the subjective feeling of anxiety than attempts to suppress or accept it.
Thoughts	Challenge assumptions	Rodebaugh et al (2009)	
 • Undergraduate students high in social interaction anxiety divided into high purposeful engagers (tend to purposefully engage with unpleasant thoughts and be open to different perspectives) and low purposeful engagers (tend not to actively engage with unpleasant thoughts or consider alternative views) • Randomly assigned to 25-min unstructured writing condition about social situation or to 25-min structured writing condition with cognitive restructuring prompts 	
 • Low purposeful engagers who did not receive cognitive restructuring prompts reported worsened mood at the end of the study, whereas low purposeful engagers who received the prompts and high purposeful engagers in both conditions did not report as much deterioration in mood.

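### The plan states that no risk can be detected, but describes no collection of unwanted effects and no by-arm summary of individual worsening, although the outcome data for such a summary are already collected in both arms

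*Combined protocol and SAP*

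**What the plan says.** The Risk/Benefit Assessment first says, with a hedge, that "the potential risk to participants is minimal or non-existent". It then adds that "There are no risks that we can detect in participating in the program". A later paragraph concludes that potential benefits outweigh potential risks.

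The hypotheses concern benefit. H1 predicts that FFW "will be more effective than the wait-list control condition in improving" overall well-being, domain well-being and health-related quality of life. H2 has the same form for self-efficacy, and H3 is mediation through improvement. The H1 method sentence begins "Analyses will test separately for differences in linear and non-linear trajectories of well-being (overall and domain specific" and goes on to name the time points and the two conditions. It states no direction or sidedness, and it does not name the SF-36v2.

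On user experience, the FFW Experience Survey has 15 items on feasibility and acceptability: "Only intervention group participants will be administered this self-report survey on one occasion after exposure to the intervention". Chat and forum logs are not systematically monitored.

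The Battery Administration Schedule gives the I COPPE Scale and the SF-36v2 to both arms at T1, T2 and T3. The SF-36v2 yields a mental component summary (MCS), and its norm-based scores have SD 10.

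**The concern.** A statement that no risk was detected means something only if someone looked. The plan defines no worsening threshold, no count of participants who worsen, no adverse-effect question and no harm analysis. The eligibility criteria do not screen on mood or health, so the program goes to unselected medical patients. Some of its writing tasks touch on difficult subjects, for example "Challenge 8: Think about the end of life".

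A difference in mean trajectories can favour FFW while some participants do worse than they would have without it. The trial could then report effectiveness and repeat that there is no risk, with nothing by arm behind the second statement. The stated benefit/risk conclusion would be untested.

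**Working it through.** The documents give no worsening rate, threshold, alpha, dropout or harm figure, so there is nothing of the plan's own to reproduce. The steps below test what the planned analyses and a simple remedy could show.

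**Inputs from the documents.** Enrolment cap 500 and 2:1 allocation, so about 333 versus 167 if the cap is reached; SF-36v2 norm-based SD 10.

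**Assumptions.** Normal scores with equal SDs, no mean change in controls, T1-T2 correlation r of 0.6 to 0.8, follow-up of 60% to 100%, and a drop of 0.5 SD (5 norm-based points) used only as an example margin.

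**Step 1: can a mean contrast hide minority worsening?** Suppose 90% gain 0.30 SD and 10% lose 0.80 SD relative to control.
- Mean effect = 0.90 × 0.30 − 0.10 × 0.80 = +0.19 SD.
- With 5% or 15% losing, the mean is +0.245 or +0.135 SD.

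The mean still favours FFW.

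**Step 2: how many controls would cross a 0.5 SD drop by ordinary variation?** The SD of change is √(2(1 − r)), and the proportion crossing is Φ(−0.5/√(2(1 − r))).
- r = 0.6: SD of change 0.894, Φ(−0.559) = 28.8%.
- r = 0.8: SD of change 0.632, Φ(−0.791) = 21.5%.

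A control rate of only 5 to 15% at this margin would need r of about 0.95 to 0.88.

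**Step 3: precision of the arm difference.** Half-width = 1.96 × √(p(1 − p)(1/n₁ + 1/n₂)), with equal rates in the arms.

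| Control rate p | 333 vs 167 | 200 vs 100 (60% follow-up) |
|---|---|---|
| 21.5% | 7.6 points | 9.9 points |
| 28.8% | 8.4 points | 10.9 points |

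**Step 4: would a threshold count reveal the minority in Step 1?** At r = 0.8, the FFW proportion crossing is 0.90 × Φ(−0.80/0.632) + 0.10 × Φ(0.30/0.632) = 0.90 × 0.103 + 0.10 × 0.682 = 16.1%, against 21.5% in controls. The same formula gives 25.3% versus 30.9% at r = 0.5 and 10.8% versus 13.2% at r = 0.9. In this example FFW has fewer threshold crossings although one participant in ten is worse off. The count alone can mislead, so the full distribution of change is needed beside it.

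**Step 5: what would a direct question give?** For assumed report rates of 5 to 15% in both arms, the Step 3 formula gives half-widths of 4.1 to 6.6 points at full follow-up and 5.2 to 8.6 at 60%. If no FFW participant reported an unwanted effect, the one-sided 95% upper limit would be 1 − 0.05^(1/333) = 0.9%, or 1.5% with 200 responders. These limits apply to responders only.

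**Step 6: what the appendix supports.** For one cited writing study it says "Low purposeful engagers who did not receive cognitive restructuring prompts reported worsened mood at the end of the study". The same row says that low purposeful engagers given prompts, and high purposeful engagers in either condition, did not deteriorate as much. The sample was undergraduates high in social interaction anxiety, in a 25-minute writing task. The neighbouring row describes a study in which writing about an interpersonal hurt lowered negative affect compared with neutral writing.

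**Step 7: how much of FFW is comparable?** In the module list, 59 of 148 skill challenges include written self-reflection. By title, about 10 of the 59 concern negative emotions, stress, faulty thinking or the end of life: three in Cope with negative emotions, four in Challenge assumptions and three in Know yourself.

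**The case against.** A reader might infer that nothing in the plan could show harm. That goes too far. The analyses test differences in trajectories, and domain well-being includes psychological well-being, so average worsening would show as a negative difference if the test is two-sided. The plan also intends to compare effects by dosage and to inspect distributions at each time point. None of this is a by-arm account of individual worsening.

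A reader might also infer that the protocol's own evidence shows FFW writing worsens mood. It does not. The appendix result concerns one subgroup in an unstructured task, FFW writing uses text prompts, another cited writing study found benefit, and most FFW writing tasks have neutral or positive subjects. What remains is narrower: the documents do not say that every exercise carries cognitive restructuring prompts, and the cited result is comparative, so it does not exclude deterioration.

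Two points of restraint also stand. The 15 Experience Survey items are not reproduced, so one may touch on unwanted effects; even then it would be asked of one arm, once. The consent pages are not in the file, so their risk wording cannot be criticised. Finally, the split in Step 1 is invented and would apply to any trial analysed by means. It shows what is possible, not what is likely here.

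**Conclusion.** The point holds in limited form. The plan declares that no risk can be detected but describes no collection of unwanted effects in both arms and no by-arm summary of individual worsening. Minority worsening would go unexamined.

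The documents do not support a claim that FFW is harmful, and a threshold count from existing scores would not settle the question. Under the stated assumptions it mixes true worsening with ordinary variation in about 21 to 29% of controls, with a half-width of 7.6 to 8.4 points at full follow-up and 9.9 to 10.9 at 60%. Such a table is descriptive, and the direct question must carry the safety information. The figures rest on assumed correlations, normality, equal SDs, stable control means and enrolment reaching 500. The textual gap does not depend on them.

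**What to change.** 1. Add one neutrally worded item at T2 and T3 in both arms asking whether anything in the study upset the participant or made them feel worse. Report counts and proportions by randomized arm, with the difference and 95% CI.
2. Prespecify in the Data Analysis Plan a descriptive by-arm display, at T2 and T3, of change from T1 in the SF-36v2 MCS and the present-time I COPPE psychological rating. Show the full distribution and the proportion falling by a margin fixed before any data are seen, with denominators, 95% CI, and counts missing through non-return or a failed attention item. Distressed participants may be the ones who stop responding.
3. State beside the display that the proportion includes ordinary score variation and cannot by itself show absence of harm.
4. Replace the sentence that no risks can be detected with one saying that transient distress from self-reflection is possible and will be described by arm. Check that the consent wording agrees.

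The cost is one item on top of the 97 common to both arms at T2 and T3 (21 + 21 + 19 + 36), one table, and a slightly less favourable risk statement. No extra participants are needed.

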2. **I COPPE Scale.** Participant well-being in I COPPE domains will be self-assessed with this measure using a validated tool called the I COPPE Scale (Myers, Prilleltensky, I., Jin, Dietz, Rubenstein, Prilleltensky, O., & McMahon, 2014; Prilleltensky, I., Dietz, Prilleltensky, O., Myers, Rubenstein, Jin, & McMahon, 2015; Myers, Park, Lefevor, Dietz, Prilleltensky & Prado, 2016). The I COPPE Scale was validated during two online studies testing the theorized seven-factor theory of well-being (six life domains as well as overall well-being) in

both a general population sample of 426 adults (214 women, 212 men), ages 20 to 88 ($M = 50.86$, $SD = 13.57$) and in a sample of 641 English-speaking Hispanic adults (354 women, 287 men), ages 19 to 83 ($M = 41.04$, $SD = 13.97$).

Prilleltensky and colleagues (2015) tested the theorized seven-factor theory of well-being (six life domains as well as overall well-being) using the I COPPE Scale and assessed the scale's construct validity using well established comparison measures. Four hundred twenty-six mostly White/Caucasian (83%) participants (214 women, 212 men) ranging in ages 20 to 88 ($M = 50.86$, $SD = 13.57$) completed the online battery of instruments. Using exploratory structural equation modeling (ESEM), this study fully and reliably assessed the underlying constructs of the **I COPPE Scale**. Findings provided strong empirical evidence of the I COPPE theoretical framework and construct validity of the I COPPE factors with correlations ranging from .43 to .74.

The I COPPE Scale was also tested in a sample of six hundred forty-one English speaking self-identified Hispanic adults (354 women, 287 men), ages 19 to 83 ($M = 41.04$, $SD = 13.97$) (Myers et al., 2016). The participants completed the survey battery of comparison instruments. Both exploratory bi-factor analysis (EBFA) and confirmatory bi-factor analysis (CBFA), were used to assess the underlying constructs of the multidimensional **I COPPE Scale**. Initial validity evidence was found with correlation values ranging from .26 to .63.

Definitions of the seven I COPPE Scale constructs and corresponding items are as follows:

a. Overall Well-being (OWB). Overall well-being (OWB) is a positive state of affairs in an individual's life. Well-being derives from satisfaction of needs in six domains of life:

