- 5) **Self-Efficacy in Well-Being Scale (SEWB).** The SEWB is a 21-item tool created for this study that measures the construct of self-efficacy in the I COPPE well-being domains in three times of present, 30-days ago, and 30-days from now. We define the construct of self-efficacy in well-being domains as the extent to which an individual believes that she/he has the capacity to achieve well-being in different domains of life (i.e. overall, interpersonal, community, occupational, physical, psychological and, economic). Directions on the scale instruct the respondent to rate each item on a 0-4 scale that ranges from no confidence to complete confidence. Each item is a phrase that completes the following stem prompt: “How confident are you in your current ability to achieve well-being in-“. Some item examples are: “your life as a whole”; “your main occupation”; “your physical health and wellness”. All

items are phrased in a positive direction. Seven scores will be derived, one for each item ranging from 0-4 per item. A high score is interpreted to mean the respondent is a person with high self-efficacy within areas of I COPPE functioning.

6) **The SF-36v2® Health Survey.** The SF-36 version 2.0 is considered the international version of the original well-established version 1.0 . Version 2.0 has been used in over 1000 studies with documented psychometric evidence for its use (Ware, 2000). The SF-36v2 measures generic functional health status using eight health-related quality of life subscales tapping: physical functioning, bodily pain, role limitations due to physical health problems, role limitations due to personal or emotional problems, emotional well-being, social functioning, energy/fatigue, and general health perceptions. Additionally, the survey yields two summary measures of physical and mental health along with a health utility index. The eight health subscales consist of 2–10 items each rated on a Likert scale. Responses are scored using scoring software that uses a regression equation and standardizes responses to population norms, yielding both a physical component summary (PCS) and mental component summary (MCS). The eight subscale scores range from 0–100 with higher scores indicating better health status. However, users are encouraged to interpret findings using norm-based scores (Mean = 50, *SD* = 10) rather than the 0–100 scores.

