H2: Self-efficacy effect: The online well-being program will be more effective than the wait-list control condition in improving I COPPE well-being self-efficacy. This hypothesis will be conceptualized within the general multilevel structural equation modeling (MSEM; Muthén & Asparouhov, 2008) framework. Analyses will test separately for differences in linear and non-linear trajectories of self-efficacy (I COPPE specific) over the assessment time points among the 2 conditions. Parameter estimates and attrition rates may inform Monte Carlo simulations (Muthén & Muthén, 2002) with 10000 replications to determine power (given sample size) for the regression of the slope growth factor on the dichotomous (i.e., treatment versus control) intervention variable (Cohen, 1988; Raudenbush & Liu, 2001).

H3: Mediating effect: The effect of the online well-being program on 1) overall well-being, 2) domain well-being and, 3) health related quality of life will be partially mediated by improvements in I COPPE self-efficacy in well-being over time.

These hypotheses will be conceptualized within the MSEM framework for assessing multilevel mediation (Preacher, Zyphur, & Zhang, 2010). The test of mediation will be based on the product of pathway (a) from the online well-being program to change in self-efficacy and (b) the pathway from change in self-efficacy to change in well-being. The product of the two pathways

IRB Study Number: TBD

Title: Patient Well-Being Research Project 01-23-17 to IRB

(a)*(b) is the indirect effect of the online well-being program to change in well-being through change in self-efficacy in well-being. We will be testing whether the product (a)*(b) is statistically significantly different from zero by constructing confidence intervals using (1) the distribution of the product method and (2) resampling methods consistent with MacKinnon, Lockwood, and Williams (2004) and Tofighi and MacKinnon (2011). We will also examine more immediate changes in well-being through self-efficacy at each time point. Parameter estimates and attrition rates will inform Monte Carlo simulations using a SAS macro to determine power (given sample size) for a true mediation effect (MacKinnon, Lockwood, Hoffman, West, & Sheets, 2002).

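### H1 and H2 test linear and undefined non-linear trajectories on thirteen or fourteen scores, with no deciding test, primary outcome, primary time point, alpha or error control

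*Combined protocol and SAP*

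**What the plan says.** H1 (Data Analysis Plan, Hypotheses and Methods) lists overall well-being, domain well-being and "health related quality of life (HRQOL) over time", without ranking them. Its test sentence reads: "Analyses will test separately for differences in linear and non-linear trajectories of well-being (overall and domain specific) over the assessment time points". Quality of life does not appear in that sentence.

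H2 uses the same form: "Analyses will test separately for differences in linear and non-linear trajectories of self-efficacy". It then limits self-efficacy to what it calls I COPPE specific, which could mean the six domains alone or the six plus overall.

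The number of scores comes from Description of Measures:
- The I COPPE Scale has seven constructs (overall plus six domains), each with three items: now, 30 days ago and 30 days ahead.
- For the self-efficacy scale, "Seven scores will be derived, one for each item ranging from 0-4 per item".
- For the SF-36v2, besides eight subscales, "the survey yields two summary measures of physical and mental health along with a health utility index".

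Two other sentences come close to naming a deciding test or outcome. The H1 and H2 paragraphs mention simulations that may be run to find "power (given sample size) for the regression of the slope growth factor on the dichotomous" treatment variable. The section on potential benefits to society says "effectiveness of the intervention will be measured using the recently validated I COPPE Scale".

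Assessments are at baseline (T1), day 30 (T2) and day 60 (T3). Access to the program ends after 30 days (Study Procedures, Participant condition group access).

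**The concern.** Nothing tells the analyst which result decides whether the program worked. The plan does not choose between slope and non-linear term, among the seven well-being scores, or between T2 and T3, and it does not say what non-linear means: quadratic, piecewise or something else. Each choice can be made after the data are seen. The slope growth factor is named only as the target of an optional power simulation, and the I COPPE Scale yields seven scores with none selected.

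Two things are at stake. The chance of a false effectiveness claim is not controlled, and the same data can support different conclusions depending on an analysis choice that the plan leaves open.

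**Working it through.** The plan has no figure to reproduce: it gives an enrolment of 500 without alpha, power, effect size, SD or dropout.

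**Inputs from the documents.** Seven well-being scores; three equally spaced assessments; 500 participants at 2:1, so about 333:167.

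**Assumed inputs.** Two-sided 5% per test; outcome correlation 0, 0.5 or 0.7; SD 1; effect 0.30 SD; equal between-wave correlation r of 0.6 (range 0.5 to 0.7); complete data unless stated.

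**1. Only the slope decides (7 tests).** Independent: 1 − 0.95^7 = 0.302. With equicorrelated normal statistics (400,000 draws) at outcome correlation 0.5 and 0.7: 0.23 and 0.18.

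**2. Both shapes tested (14 tests).** The result depends on how the two tests are related, which the plan does not fix.
- Independent shape tests: 1 − 0.95^14 = 0.512; at 0.5 and 0.7, 0.41 and 0.32.
- Joint quadratic model with time coded 0, 1, 2: the linear coefficient is −1.5·T1 + 2·T2 − 0.5·T3 and the quadratic is 0.5·T1 − T2 + 0.5·T3. Their correlation is −3/√(6.5 × 1.5) = −0.96. The same simulation with this correlation gives 0.37, 0.28 and 0.22.

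**3. Adding H2.** With both shapes, six or seven self-efficacy scores bring the total to 26 or 28 tests. If all are independent, 1 − 0.95^26 = 0.74 and 1 − 0.95^28 = 0.76. These are upper-end values, for the reason in step 2.

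**4. Dependence on the undefined shape.** Take a benefit of 0.30 SD at both T2 and T3, with f = 1/333 + 1/167 = 0.00899 and r = 0.6.
- Quadratic: effect 0.5 × 0.30 − 0.30 = −0.15; variance 1.5(1 − r)f = 0.00539; |z| = 2.04; significant 53% of the time.
- T1–T2 segment: effect 0.30; variance 2(1 − r)f = 0.00719; z = 3.54; 94%.
- T2–T3 segment: effect 0; 5%.

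**5. What the linear slope estimates.** With complete, equally spaced data the slope is (T3 − T1)/2, so its arm difference is half the arm difference in T1-to-T3 change. A T3 contrast is therefore implied. T2 has weight zero, so an effect present at T2 and gone by T3 gives a slope difference of zero. The T2 difference is recoverable by combining linear and quadratic terms, or from a piecewise model with a knot at T2, but neither is planned for H1 or H2.

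**6. Power of the alternatives.** Testing T2 and T3 at 2.5% each was compared with testing either shape at 2.5%, both with equal baseline means. The effect was sustained, half-faded, fully faded or late-only, over r = 0.5 to 0.7 and 0 to 30% attrition. The largest gap in favour of T2/T3 is about 8 points (81.6% against 73.5%; half-faded, r = 0.5, 30% attrition). The largest gap against is about 4 points (fully faded, r = 0.6, 30% attrition).

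**The case against.** A trajectory model fits a hypothesis worded as change over time and need not have a single primary time point. That is right. The defect is that no trajectory contrast is named to decide either.

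Testing separately could mean separately by outcome, with one shape each. The wording allows it, and the 30/23/18% figures then apply. A deciding outcome and error control are still missing.

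The false-positive rates assume that any one significant score supports a single effectiveness claim. A sponsor may prefer separate claims by domain, which is legitimate if stated in advance. The plan states neither rule.

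Four stronger readings are tempting, and the documents do not support them:
- A reader might infer that nothing planned addresses lasting benefit at T3. Under step 5 the linear slope does; only the T2 difference at the end of access lacks a planned contrast.
- A reader might take 51% as the error rate. It is the upper end of a range, because it needs independent shape tests and uncorrelated outcomes.
- A reader might infer that tests at T2 and T3 are generally more powerful. Step 6 shows gaps in both directions, so no general gain is claimed.
- A reader might take the mention of changes at each time point as a planned T2 or T3 comparison. That sentence belongs to H3 and concerns mediation.

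**Conclusion.** The point holds and the sponsor should act on it. The trial can run as designed, but H1 and H2 have no decision rule. Even on the reading kindest to the plan, with the slope alone deciding, the chance of at least one false well-being finding is 18 to 30%, against a nominal 5%; testing both shapes widens this to 22 to 51%. The gap in the text is certain. The sizes are illustrative, since alpha, correlations, effect size and attrition are assumed. The dependence on shape is a separate problem that adjusting for multiple tests would not cure.

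**What to change.** 1. State the alpha. Name as the single primary test the arm difference in overall well-being at T2 or at T3; the sponsor chooses which. Estimate it with time as categorical, unstructured covariance and equal baseline means across arms, which fits within the planned structural equation framework.
2. Before unblinding, state which overall well-being item or composite is the outcome: now, 30 days ago or 30 days ahead. At T2 the item on 30 days ago refers back to baseline. Apply the same rule to the domain and self-efficacy scores.
3. If the primary is significant, test nine secondaries with Holm: overall well-being at the other time point, plus the six domains and the SF-36 physical and mental summaries at the primary time point. Add one named self-efficacy score if a confirmatory H2 claim is wanted.
4. If two primary time points are preferred to one, write the full rule: the time point of each secondary, and the alpha passed on when one or both primaries succeed.
5. Define the non-linear form, and label the growth models and all remaining tests exploratory.

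This changes analysis-plan wording only and needs no new data. Domain claims become harder. With variance (1 − r²)f at r = 0.6, moving from 5% to the strictest Holm step (0.05/9) cuts power from 98% to 88% for 0.30 SD and from 75% to 45% for 0.20 SD. A single-time-point primary has only 5% power for an effect confined to the other time point, so that choice must be deliberate.
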